- 1) Potential participant has a diagnosis of autism spectrum disorders, history of seizure disorder or seizure episodes within the last 2 years
- 2) Potential participant is receiving psychotherapy at the time of randomization
- 3) Potential participant has a history of mental retardation, pervasive developmental disorder, head trauma, traumatic brain injury, or other neurological disorder that impairs cognition
- 4) Potential participant has medical illnesses deemed to interfere with participation in study activities and/or unstable and/or untreated conditions that may affect cognition, including substance abuse/dependence disorders, ongoing chemotherapy or other cancer treatment.
- 5) Potential participant has history or current DSM-IV diagnosis of organic mental disorder, schizophrenia, schizoaffective disorder, delusion disorder, psychotic disorder NOS, bipolar disorder, substance dependence (<1 year), and/or mood congruent or mood incongruent psychotic features or disorders
- 6) Potential participants had significant medication changes, including changes to anxiety medications or other psychiatric medications, in the 4 weeks prior to screening
- 7) Potential adult participant scores less than a 14 (75%) on the University of California, San Diego Brief Assessment of Capacity to Consent (UBACC). Please note, this criteria applies only to adult participants, age 18, at the time of screening.
- 8) Potential participants who have answered 'yes' to:
 - a. Question 5 (Active Suicidal Ideation with Specific Plan and Intent) on the Columbia-Suicide Severity Rating Scale (C-SSRS), or,
 - b. Any of the suicide-related behaviors (actual attempt, interrupted attempt, aborted attempt, preparatory act or behavior) on the C-SSRS "Suicidal Behavior" portion will be excluded from the study *if the ideation or behavior occurred within 2 months from Participant's date of consent* (as recommended by the FDA for treatment trials.) Participants excluded for this reason will be referred for appropriate treatment. Further, the C-SSRS form will also be administered to all participants at the follow-up visit. Participants meeting these criteria at any time throughout the study will be asked to complete a final assessment, if appropriate, then withdrawn from the study and referred for appropriate treatment.

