Participants will be allowed as much time as needed, with Site Study personnel or in private, to review the HIPPA waiver and consenting documents before making the decision to participate. Potential participants may invite a friend or family member to be present during the visit, to further discuss their decision to enroll and/or contact (e.g., phone call) a friend or family member that is not physically present for discussion before deciding to enroll. At the potential participant’s request, Site Study personnel may be asked to ‘step-out’ of the room or end/mute the call during remote discussions, to provide privacy for such discussions. In addition, potential participants will be provided the option to defer their decision to allow them to review the consent form and other study information forms at their convenience, and later reconnect with the Site Study team remotely or return to the Study Site to enroll (i.e., complete the informed consent procedures). No study activities will take place prior to completion of the consenting process.

Participants will not be invited for consent discussions during periods of greater impairment. Participants must have been in outpatient status and on stable medications for 4 weeks prior to signing assent/consent. If a participant is hospitalized for psychiatric reasons during the study, they will be withdrawn from study activities. Additionally, consent to continue in the study will be addressed as needed throughout the study and the participant will be reminded that their participation in this study is completely voluntary and they do not have to continue unless they choose to.

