If the participant does not complete the study or withdraws early for any reason, the participant will only be compensated for the study visits and/or treatment sessions they have completed.

All participants will receive compensation for the *Screening* assessment visit (V0) after the end of the visit, regardless of eligibility. For participants who are loaned a mobile device for the duration of the intervention period, compensation for all study activities completed from V1 through V3, including the intervention period, will occur after the participant returns the loaned device to the Site Study personnel. If participants are unable to meet with Site Study personnel in person to return the device, the participant will be sent a pre-paid label and box (if necessary) to return the mobile device at no cost to them. Participants who withdraw from the study will be compensated for all study visits they have completed once the loaned device has been returned to the Site Study personnel. For participants who do not return the device,

all forms of appropriate means and communication (e.g. phone contact, email, mailed letters) will be used in an effort to retrieve the study device. The mobile device that is loaned out may have GPS enabled as part of the Find My Device feature that will allow the Site Study personnel to ping the device if the participant needs assistance with locating it. This feature will also be used to remotely deactivate a device so that the device is unusable, and/or erase the contents of the iPad, when necessary and if a loaned study device is not returned to the Site Study personnel at the end of the study.

Participants who do not return the study device will receive their compensation after Site Study personnel have exhausted all means of contact in an attempt to return the device (a maximum of three months after the end of study participation). Participants will not face any legal or financial retribution for failure to return the study mobile device.

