If participants were loaned a mobile device to complete study activities at home and no longer wish to participate in study activities, including their post-intervention interview, Site Study personnel will attempt to coordinate with the participant to return the device at a time that is convenient for the participant. If participants are patients at the Child and Adolescent Anxiety Clinic or associated UMP Psychiatry Clinics, Site Study personnel may attempt to meet them before or after a regularly scheduled clinic appointment to return the loaned device. If the participant cannot be reached, Site Study personnel will send them a letter asking them to return the device along with a box with a return label. Participants will be invited to come back for a follow up visit in this letter, but also reminded that they are free to no longer participate in the study. Site Study personnel may also send this letter to participants who completed all study

activities but forgot to return the device and are unable to coordinate with Site Study personnel to return it.

8. *Exit Survey* (~10 minutes): Participants will be asked to fill out an online exit survey to rate enjoyment, usability, perceived benefits, and ease of fit into schedule.

Assessments.

The complete assessment battery will be performed at the pre-intervention assessment (*Baseline Assessment*, V1) visit and at the post-intervention assessment (*End of Study*, V3) visit. For a full list of all assessments and administration times, please direct your attention to the *Description of Assessments* or *Appendix I*. We will use assessments of functional abilities to determine the degree of transfer of benefit to real-world experience (e.g., symptoms, social functioning, quality of life).

All assessments will be administered to all participants; alternate forms of the assessments will be used when available to mitigate test-retest effects. Performance on all measures will be scored, submitted into the study database, and monitored for accuracy and integrity. Any discrepancies in scoring will be resolved by referring to the raw data collected during the assessment visit(s).

Description of Assessments

Diagnostic Assessment

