Study participants may withdraw from the study at any time, for any reason, or for no stated reason. We anticipate that a common reason for study withdrawal will be the time required to complete the intervention. For participants seeking to withdraw for that reason, we will offer the alternative of discontinuing the intervention and scheduling and completing the post-intervention assessment (*End of Study, V3*) visit, given they have met the minimum sessions required to complete the post-assessment visits. The data analysis plan is structured so that their data will be valuable even if they do not complete the intended number of sessions. Participants who still wish to withdraw following that option will withdraw. Other than time required to use the program, we do not anticipate any common reasons for withdrawal that we will plan for in advance.

In rare cases, a Principle Investigator may decide to prematurely discontinue a participant's involvement in the study for any of the following reasons:

- a) Safety,
- b) Participant non-compliance,
- c) A change in circumstance that would prevent completion of protocol-required assessments,
- d) Participant relocation to an area that, due to great distance, would prohibit a participant from receiving follow-up at the study site,
- e) Participant displays inappropriate behavior toward study staff members or other participants,
- f) Participant is hospitalized for psychiatric reasons;
- g) Loss of funding, or;
- h) A clinical determination, by the Principal Investigator, that continuation in the study is not in the participant's best interests.

Across all reasons for withdrawal, we will ensure an orderly end to the participant's involvement in the study by arranging for the Site Study Coordinator or WASABI Clinician to recover the mobile device (if it has been issued to the participant), conducting an informational interview with the participant to understand the reasons for study withdrawal and identify any issues with study conduct or adverse events that are relevant, and arrange study compensation for sessions that the participant completed.

Modifications to the Protocol

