The Site Study Coordinator and WASABI Clinician will ask about any deterioration in symptoms during each contact with participants, and will be alert to any volunteered episodes of suicidality. All events of this nature will be documented on a standardized form and will be classified by the PI to their degree of seriousness and their relationship to the study protocol. Participants will be referred to appropriate clinical care should there be any concerns for safety or increasing symptoms. If deemed clinically necessary, the PI may elect to remove participants from the study if they find that it is no longer in the participant's best interests to continue participation in the study.

Finally, we will also conservatively follow guidelines for medical devices (i.e., computerized assessments) in the reporting of adverse events in this trial, which defines unanticipated adverse device effects (UADEs) in The Code of Federal Regulations in 21 CFR 812.3(s) as any serious adverse effect on health or safety associated with, a device.

Continuing Review and Final Report

In accordance with NIA SBIR guidelines, a continuing review report(s) as well as a Final report will be submitted via eRA Commons.

The knowledge of any pending compliance inspection/visit by the FDA, Department of Health and Human Services Office for Human Research Protection, or other Government agency concerning clinical investigation or research, the issuance of Inspection Reports, FDA Form 483, warning letters, or actions taken by any Regulatory Agencies, including legal or medical actions, and any instances of serious or continuing noncompliance with the regulations or requirements will also be reported.

Surveys, Questionnaires and Other Data Collection Instruments

*Complete paper versions are available upon request.

Diagnostic Assessment

MINI-KID

<https://eprovide.mapi-trust.org/instruments/mini-international-neuropsychiatric-interview-for-children-and-adolescents>

Cognitive Status

WASI-II

<https://www.pearsonassessments.com/store/usassessments/en/Store/Professional-Assessments/Cognition-%26-Neuro/Wechsler-Abbreviated-Scale-of-Intelligence-%7C-Second-Edition/p/100000593.html>

Anxiety and Social Anxiety

SPAI-B

<https://www.mhs.com/MHS-Assessment?prodname=spai>

LSAS-CA

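### Removal for psychiatric hospitalisation or safety has no clear end-of-study assessment, so secondary outcomes can be lost for symptom-related reasons

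*Protocol*

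**What the plan says.** **Hospitalisation.** Protocol, Description of Informed Consent Process: "If a participant is hospitalized for psychiatric reasons during the study, they will be withdrawn from study activities". Protocol, Withdrawal from the Protocol, lists psychiatric hospitalisation as item f under a discretionary opening: "In rare cases, a Principle Investigator may decide to prematurely discontinue a participant's involvement in the study for any of the following reasons". Items a (safety) and h (best interests) fall under the same opening.

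**Other safety removals.** Protocol, Reporting of Serious Adverse Effects & Unanticipated Device Effects: "If deemed clinically necessary, the PI may elect to remove participants from the study". No outcome assessment is mentioned.

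**Close-out.** For all withdrawals, the withdrawal section lists device recovery, compensation and "conducting an informational interview with the participant to understand the reasons for study withdrawal and identify any issues with study conduct or adverse events". V3 is not on the list.

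**C-SSRS events.** Exclusion criterion 8, repeated under Screening Procedures, is different: "Participants meeting these criteria at any time throughout the study will be asked to complete a final assessment, if appropriate, then withdrawn from the study".

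**Other routes to V3.** For people who want to leave because of the time required, the withdrawal section says: "For participants seeking to withdraw for that reason, we will offer the alternative of discontinuing the intervention", followed by V3 if the minimum sessions were met. Description of Protocol Devices gives a similar route, with the same condition, to participants who choose to stop using the program. The device-return text in Study Procedures/Research invites back participants with a loaned device who cannot be reached.

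**Outcomes and model.** Appendix I schedules LSAS-CA, SPAI, MASC-2, SSQ and ASSES at V1 and V3 only. SAP section (2) lists SPAI-B, not SPAI, as the self-report outcome. Under Intervention Embedded Assessments in the Protocol, the weekly SPAI-B is given to the WASABI arm only. The SAP model has time, group, their interaction and a random subject intercept, and assumes data missing at random (MAR).

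**The concern.** Two things are unsettled. First, the same event triggers mandatory withdrawal in one section and a discretionary decision in another. Second, neither section says whether V3 follows. A site could reasonably obtain V3 or not, and could do so differently from one participant to the next.

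The participants at issue are those whose symptoms probably worsened. If their V3 is not collected, the missingness is plausibly related to the unseen outcome. The SAP model uses baseline score and arm but knows nothing of the hospitalisation or safety stop, so it predicts these participants' V3 as if they resembled others in the same arm. That makes the arm that lost the participant look better than it was. The SAP puts its weight on the between-arm effect size, and the Protocol intends these data to help power Phase II, so the direction of any such error matters even in a pilot.

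**Working it through.** **Step 1. Does the text say V3 is lost?** The consent section stops study activities. The Protocol uses that term in two ways:

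- Including V3: the compensation text speaks of "compensation for all study activities completed from V1 through V3, including the intervention period", and the device-return text of participants who "no longer wish to participate in study activities, including their post-intervention interview".
- Intervention only: item 6 of Study Procedures/Research, the extra-time provision in Description of Protocol Devices, and the Active Control Program description, which compares time spent by arm.

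Both readings are open, so V3 after hospitalisation is undetermined.

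**Step 2. Does another clause reach these participants?**

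| Route | Reaches hospitalisation or safety removals? |
|---|---|
| C-SSRS rule | Only if C-SSRS criteria are met |
| V3 offer for time burden | No |
| Participant-chosen cessation | No; an investigator's removal is not the participant's choice |
| Device-return letter | Not tied to these removals |
| SAP effort to assess all above minimum activities (2 calls, 5 EMAs) | Possibly; silent on whether it survives withdrawal, and placed under a WASABI-arm outcome |

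A gap remains for removals that do not meet the C-SSRS criteria.

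**Step 3. Size of the effect on d.** The SAP defines d as the difference in mean change divided by the pooled baseline SD. Inputs:

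- Arm size: 12 completers planned per arm (Protocol, General Study Design); 8 in the control group (SAP section 2).
- m: number removed without V3 in one arm. The documents give no expected number.
- δ: gap between true and MAR-predicted V3, in baseline SD. Assumed 0.5, 1.0 and 1.5.

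Shift in d ≈ (m/n) × δ, where n includes the removed participants.

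| Case | m/n | δ = 0.5 | δ = 1.0 | δ = 1.5 |
|---|---|---|---|---|
| One, in addition to 12 completers | 1/13 | 0.038 | 0.077 | 0.115 |
| Two, in addition to 12 completers | 2/14 | 0.071 | 0.143 | 0.214 |
| One, among the 8 controls | 1/8 | 0.063 | 0.125 | 0.188 |
| One, in addition to 8 controls | 1/9 | 0.056 | 0.111 | 0.167 |

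Simulation with a maximum-likelihood, two-time-point random-intercept model (600 trials per case, δ = 1, pre-post correlation r = 0.6) agrees: 0.078, 0.149, 0.130 and 0.112 for the four rows. With one participant lost from each arm (13 v 9), the net shift is 0.031, against 1/9 − 1/13 = 0.034 by formula.

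**Step 4. Compare with sampling error.** SE of d ≈ √(2(1 − r)) × √(1/12 + 1/8), with r assumed:

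- r = 0.4: 0.500
- r = 0.6: 0.408
- r = 0.8: 0.289

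At r = 0.6, one removal amounts to between 0.038/0.408 = 9% and 0.188/0.408 = 46% of one standard error.

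**The case against.** The strongest reply is that the two hospitalisation rules may be compatible: stopping the intervention is mandatory and ending study involvement is discretionary. That reading is coherent and close to what is recommended below. It stands as a possible reading, but neither section states it, and the compensation and device-return texts point the other way. For the same reason, a reader who infers that the Protocol cancels V3 after hospitalisation goes too far.

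Second, much is already covered. Removals meeting the C-SSRS criteria get a final assessment if appropriate, and the C-SSRS may be repeated during the intervention when safety is a concern. This stands and narrows the gap; it would be wrong to say that all safety removals lack a final assessment. The as-needed C-SSRS does not supply the efficacy scales. For SPAI-B, a removed WASABI participant may have weekly scores up to removal. A control participant has none between the baseline and end-of-intervention sessions.

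Third, a reader might infer that the Protocol breaks its commitment not to restrict analyses to fully adherent participants. It does not. That sentence in Data Analysis concerns adherence, and under full information maximum likelihood a participant with baseline data only stays in the analysis. What suffers is the plausibility of the MAR assumption for that participant.

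Fourth, the size is small and rests on an assumed δ. The Protocol calls investigator discontinuations rare, and eligibility excludes recent hospitalisation, recent medication changes and recent serious suicidality. This also stands, and limits the weight of the point.

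**Conclusion.** The point holds as a cheap improvement. The hospitalisation rule is mandatory in one place and discretionary in another, and V3 is not clearly provided for after hospitalisation or investigator-led safety removal outside the C-SSRS criteria. Loss of V3 for these reasons is plausibly outcome-related, and the SAP model does not carry the event.

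For one removal the shift in d is about 0.04 to 0.19, favouring the arm that lost the participant, against an SE of about 0.41 (0.29 to 0.50 over the assumed correlations). This depends on δ between 0.5 and 1.5 SD, on V3 not being obtained, and on the loss falling in one arm. It is zero if nobody is removed or V3 is obtained, and largely cancels if each arm loses one.

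A reader might infer a threat to the trial's main aim. The documents do not support that: the primary outcomes are feasibility measures reported descriptively, the affected scales are secondary, and the SAP de-emphasises hypothesis testing. Assessment adherence is a primary outcome, but a missed V3 would simply be counted there, not distort it.

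**What to change.** 1. In the consent section and in item f of the withdrawal section, state one rule: psychiatric hospitalisation ends the intervention. State that safety removals by the investigator (items a and h, and the adverse-effects section) do the same, and that none of these ends outcome follow-up.
2. Add V3 to the close-out list. Attempt it at the scheduled post-intervention time, or as a final assessment at removal if later contact is unlikely, unless consent or assent is withdrawn or assessment is clinically inappropriate.
3. Treat the minimum-session condition consistently: apply it equally to these participants and to those who stop by choice, or drop it for everyone in the ITT population. Waiving it for this group alone would have no clear rationale.
4. Report by arm the number of safety stops and whether V3 was obtained.

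The cost is a wording amendment with IRB review and matching consent and assent text, two extra columns in the disposition table, and about 2 hours and $75 per case (the Protocol's V3 duration and payment). The main downside is some burden on an unwell adolescent, which the clinical exemption limits. The SAP is partly in the past tense and gives the control group size, so conduct may be advanced. If so, item 4 is still feasible and the wording can carry into Phase II.

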Participants expressing interest in the study that do not meet certain eligibility criteria, e.g. have experienced a change in medication or have been hospitalized within the last 4 weeks, have an upcoming medical procedure, surgery or treatment that would interrupt their participation, have experienced suicidal ideation or behavior within two months or those with known future end dates to psychotherapy treatment, will be placed on hold and re-screened for appropriate eligibility criteria.

Study Procedures/Research

Study Procedures: Participants at the recruitment Site will flow through the study in the following manner:

1. *Informed Consent Discussion:* Site Study personnel will discuss study goals, activities, and requirements with the parent/legal guardian and/or potential participant; complete the informed consent discussion, and if/when appropriate the potential participant will complete assent/consent to join study.
Duration: ~30-60 minutes remotely or in-person at the Study Site.
2. *Initial Screening Visit (V0):* Following assent/consent, Site Study personnel will perform diagnostic assessments and interviews and assess inclusion/exclusion to determine if the participant is eligible for enrollment.
Duration: ~2-3 hours remotely or in-person at the Study Site. The *Informed Consent Discussion* and the *Initial Screening Visit (V0)* may occur independently or may be combined in a single session.
3. *Baseline Assessment (V1):* Following enrollment, the participant will perform all social/cognitive baseline characterization assessments and questionnaires prior to the intervention period. Duration: ~2 hours remotely or in-person at the Study Site.
4. *Randomization:* Participants will be randomized into one of two treatment groups.
5. *Mobile device Set-Up and Proctored Application Use (V2):* The participant will be oriented to the intervention activities and program application(s). Participants assigned to both WASABI and the active control arm will complete a series of mobile assessments during this visit (embedded baseline assessments via BrainHQ) .

Participants with a compatible personal device that are willing to download the necessary application(s) for program use will have their device set-up at this visit. Participants assigned to WASABI will be guided to schedule reminders for

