completing their study activities. Participants that do not have a compatible personal device, do not wish to use their personal device, or do not agree to configure their settings and download the necessary application(s) for program use will be loaned a mobile device for the duration of the *Intervention and Program Use* period. Participants will be asked to sign a form acknowledging they have been loaned a study device. The research team may attempt to complete this visit on the same day as *Baseline Assessment (V1)*, but a separate visit may be scheduled, if necessary.

Duration: ~30-60 minutes remotely or in-person at the Study Site.

6. *Intervention and Program Use*: Participants will have a 1:1 orientation with the WASABI Clinician prior to engaging in their assigned group intervention activities. Site Study personnel will review the *Procedures and Guidelines to Group Therapy* and will ask the parent/legal guardian and/or participant to review and sign this form. After which, participants will remotely engage in the intervention for 12 weeks, completing approximately 12 hours of dCBGT in addition to other assigned study activities.
7. *Post-Intervention Assessment (End of Study Visit; V3)*: After the *Intervention and Program Use* period is completed, the participant will be asked to complete their final assessment visit, where they'll repeat all assessments performed at baseline to assess changes in performance.

Duration: ~2 hours remotely or in-person at the Study Site.

Participants expressing interest in returning their device to its original settings will be instructed by Site Study personnel on how to delete study application(s) during this visit or at the time of study exit. Participants loaned a study device will be asked to return the loaned device at this visit.

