Digitally delivered Cognitive Behavioral Group Therapy (dCBGT): The WASABI Clinician will lead weekly dCBGT structured sessions through videoconferencing. Sessions replicate the protocol described in "Cognitive-behavioral group therapy for social phobia in adolescents",⁵⁴ with 12 weekly sessions that center CBT content around the young person's developmental context, needs, and capacities, and adapt it to the unique developmental issues characteristic of adolescence (e.g. ascendancy of the peer group, identify formation, propensity towards limit testing). Sessions 1-4 focus on psychoeducation on recognizing and understanding social anxiety symptoms (e.g., avoidance cycle that maintains anxiety over time; rationale for exposure to overcome avoidance cycle). Sessions 5-6 implement cognitive restructuring (focusing on the identification/modification of dysfunctional thoughts) and social skills training. Session 7-8 include instruction in exposure principles and role-play/modeling of exposure exercises. Sessions 9-11 focus on in vivo exposure to anxiety provoking situations. In vivo exposure during these sessions focuses on anxiety provoking situations that can be created within the social setting of the video chat, such as a person giving a speech or singing a song, members engaging in "small talk" with each other, or people altering their appearance in a socially conspicuous way (e.g., messy hair, wearing silly attire). Session 12 focuses on how to avoid personal pitfalls and relapse. Adjustments may be made to the dCBGT treatment

described in “Cognitive-behavioral group therapy for social phobia in adolescents” during COVID-19 to allow for a more appropriate treatment given current shelter-in-place and distance-learning procedures that may not allow for replication of the traditional protocol. Participants are assigned “homework” focused on practicing specific skills in anxiogenic, in vivo situations to promote skills generalization and anxiety/fear extinction learning.

Participants in the active control will complete two sessions of embedded assessments, one immediately before and one after the 12-week intervention. The embedded assessments include two cognitive assessments—an attention bias assessment and interpretation bias assessment—and the SPAI-B assessment.

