7. Reported side effects (raw score). *Based on our previous findings, we expected 0 adverse events due to program use).*

The secondary outcome measures were collected by trained personnel blind to treatment assignment at baseline and after the intervention:

- clinician ratings of anxiety and social anxiety symptoms through the Liebowitz Social Anxiety Scale for Children and Adolescents (LSAS-CA)
- self-report inventories of social anxiety symptoms through the Social Phobia and Anxiety Inventory-Brief (SPAI-B) – at baseline, weekly during the intervention, and after the intervention;
- a broad measure anxiety and potential generalization of treatment to other anxiety domains, the Multidimensional Anxiety Scale for Children 2nd Edition (MASC-2);
- social skills by administering the Social Skills Questionnaire (SSQ) ;
- social functioning using the Adolescent Social Self-Efficacy Scale (ASSES).

The criterion for statistical significance is $p < 0.05$. Results with $p < 0.1$ will be described as trends.

The primary analysis time point is the post-intervention assessment.

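### The embedded BrainHQ baseline (attention bias, interpretation bias, SPAI-B) is taken at V2, after randomisation, and for the two bias tests no pre-allocation value is documented

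*Protocol*

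**What the plan says.** The General Study Design section of the protocol has participants establish their baseline first and be randomised afterwards. Study Procedures follows that order for V1: "Following enrollment, the participant will perform all social/cognitive baseline characterization assessments and questionnaires prior to the intervention period" (step 3). Step 4 reads "Participants will be randomized into one of two treatment groups". Step 5 is V2, the device set-up visit. There, "The participant will be oriented to the intervention activities and program application(s", and participants, by then described by arm, "will complete a series of mobile assessments during this visit (embedded baseline assessments via BrainHQ". For one arm only, the step adds: "Participants assigned to WASABI will be guided to schedule reminders for" their study tasks. On timing it says "The research team may attempt to complete this visit on the same day as" V1.

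The Active Control Program section defines the content: "The embedded assessments include two cognitive assessments", namely attention bias and interpretation bias, plus the SPAI-B. Intervention Embedded Assessments has both arms take the embedded set just before and just after the 12 weeks.

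That section and Data Analysis propose the two bias tests as possible moderators and mediators. The SAP mentions a set of mediators and moderators but names no measure, visit or model for them. It lists SPAI-B as a secondary outcome measured at baseline, weekly and after the intervention, without saying which visit supplies the baseline. Of the secondary outcomes as a group it says "The secondary outcome measures were collected by trained personnel blind to treatment assignment at baseline and after the intervention".

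**The concern.** A moderator should be measured before allocation, so that it cannot itself respond to the arm assigned. The same holds for the first value of any change score compared between arms. If participants in one arm react to what they learn or see at V2, and those in the other arm react differently, the difference is stored in the pre value. It then reappears, with the sign reversed, as a between-arm difference in change.

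Three uses are exposed to different degrees: the bias tests as moderators, any two-arm comparison of change in bias, and the SPAI-B change if the SAP's baseline is the V2 value. SPAI-B is a self-report scale, so expectation is a plausible influence. The SAP gives weight to the standardised effect size rather than to p-values, and the protocol intends to use these data to power the next trial. A distortion of the point estimate would therefore be carried forward.

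**Working it through.** The plan gives no figure to reproduce, because the point concerns the order of visits. Setting the passages side by side:

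| Measure | Pre value | Relative to randomisation | Post value | Planned use |
|---|---|---|---|---|
| LSAS-CA, SPAI, MASC-2, SSQ, ASSES | V1 (Appendix I) | Before | V3 | Protocol secondary outcomes (the SAP lists SPAI-B where the protocol lists SPAI) |
| Attention bias, interpretation bias | V2 only; absent from Appendix I | After | Embedded session after the 12 weeks, both arms | Possible moderators and mediators |
| SPAI-B | Screening (eligibility, 25 or more) and V2 | Before and after, respectively | Embedded session after the 12 weeks, both arms; also weekly in the WASABI arm | SAP secondary outcome, baseline visit not named |

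1. **Timing.** V1, randomisation and V2 are steps 3, 4 and 5. The individual orientation with the clinician and the first group session belong to step 6. The embedded baseline is therefore post-allocation but pre-treatment. Holding V1 and V2 on one day shortens the gap but leaves the order unchanged.

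2. **Bias tests.** Step 3 speaks of all baseline assessments, but no bias test is listed at Screening or V1. V2 is the only documented baseline for them.

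3. **SPAI-B.** Appendix I shows it at Screening only. The only documented post-intervention SPAI-B in the control arm is the embedded one, and the matching embedded pre value is V2. The SAP's wording allows either Screening or V2 as the baseline.

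4. **How a reaction would pass through.** Let the V2 value be shifted by a in the WASABI arm and by c in the control arm, with post values unaffected. Then
   - observed change (WASABI) = true change − a
   - observed change (control) = true change − c
   - observed difference in change = true difference − (a − c)

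   The SAP's effect size divides the difference in change by the pooled baseline SD, so the error in d is −(a − c)/SD. For illustration only, an assumed a − c of 0.1 to 0.3 baseline SD moves d by 0.1 to 0.3 in the opposite direction. If a = c, the error in the difference is zero.

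5. **Mediation.** Data Analysis confines this model to the active group and relates outcomes to improvement on the bias tests. A between-arm shift (a − c) does not enter it directly. Within that arm, a shift common to everyone changes the mean improvement but not its association with outcome; only person-to-person variation in the reaction would.

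**The case against.** The case on the other side is substantial.

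- **The values precede treatment.** This stands. No therapy has been given by V2, so the question is limited to reaction to allocation or set-up.
- **The order within V2 is not stated.** A reader might infer that the tests follow arm-specific orientation. The documents do not say so: the one arm-specific task named, scheduling reminders, appears after the sentence on the tests. They do not exclude it either, so the risk is uncontrolled rather than shown.
- **Participants are meant to be blind.** The Blinding section has both arms described to participants as forms of the same group therapy. That weakens the mechanism, although set-up that differs by arm may weaken the blind in turn. A speeded letter task and an image choice are also less obviously open to expectation than a self-report scale.
- **Few planned analyses depend on it.** A reader might infer that arm-by-baseline interactions become uninterpretable. Neither document specifies such an interaction, and the bias tests are not primary or secondary outcomes. What remains is a stated intention to examine them as moderators, plus the SPAI-B ambiguity.
- **SPAI-B has a pre-randomisation value.** This stands. Naming Screening as the baseline would put the SPAI-B pre value before allocation.
- **The staff at V2.** A reader might infer that whoever sets up the arm cannot be the blind collector the SAP describes. The protocol does not say who runs V2, and participants complete the tests themselves in the app. The passages need reconciling, but a breach of blinding does not follow.
- **Sampling error is larger.** With 12 per arm, the standard error of a between-arm difference in baseline means is √(1/12 + 1/12) = 0.41 SD, above the assumed 0.1 to 0.3. That is correct, but chance imbalance averages zero and is reflected in the confidence interval; a differential reaction is not.

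**Conclusion.** The point holds as a defect of sequence. The embedded baseline is post-allocation and pre-treatment, out of step with the protocol's own design statement and with the V1 timing of the other scales. For the two bias tests no earlier value is documented, so their use as moderators, and any two-arm comparison of change in them, could be affected by a reaction to allocation. For SPAI-B the exposure depends on which visit the SAP means. If it means V2, any differential reaction passes into the difference in change one for one.

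The size cannot be estimated from the documents; the 0.1 to 0.3 SD above is an assumption, and zero is possible. The feasibility outcomes assessed in the WASABI arm and the scales with a V1 baseline are untouched, and the active-group mediation model is not directly affected by a between-arm shift. A reader might infer that the trial's efficacy results are biased as a whole; the documents do not support that. This is an avoidable weakness in exploratory analyses and possibly in one SAP secondary outcome, worth correcting because the correction is cheap.

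**What to change.** 1. Complete the embedded BrainHQ set before randomisation: at the end of V1, or, when V1 and V2 fall on one day, by randomising only after these tests are done. Keep orientation and arm-specific set-up after that point.
2. Add the embedded set to Appendix I at its pre and post visits.
3. State in the SAP which SPAI-B is the baseline, and reconcile the sentence on blind collection with self-completion in the app.
4. Label values already collected at V2 as post-randomisation, pre-treatment, and do not use them as moderators.

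No new assessment is needed, and no sample size, power or alpha figure changes. Both arms already use BrainHQ for these tests, so installing it earlier need not reveal the allocation. The costs are a short amendment, a slightly longer V1, and having the app, login and any loaned device in place before allocation, including for remote participants. The gap between the tests and the start of the intervention may also lengthen, because cohorts of 3 to 6 are assembled after baseline and randomisation, whereas the protocol wants these tests close to the start.
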